4.2.4 Dates and times

Partial dates may be imputed for the following reasons:

- Classification of AEs as treatment-emergent
- Classification of medications as prior or concomitant

Imputed dates will not be shown in the listings; all dates will be displayed as reported in the database.

The following rules will be applied for partial start dates:

- If only the month and year are specified and the month and year of the first dose of study medication is not the same as the month and year of the start date then use the 1st of the month, or the date of screening if this is later (if the latter imputation results in an end date that is earlier than the start date, then use the 1st of the month). If time is missing this will be imputed as 00:00h
- If only the month and year are specified and the month and year of the first dose of study medication is the same as the month and year of the start date, then the date of the first dose of study medication will be used. If this results in an imputed start date that is after the specified end date, then use the 1st of the month, or the date of screening if this is later (if the latter imputation results in an end date that is earlier than the start date, then use the 1st of the month). If the imputed date is the date of dosing then time will be imputed as the start time of the dosing (i.e., event will be regarded as treatment-emergent)
- If only the year is specified, and the year of the first dose of study medication is not the same as the year of the start date then January 01 will be used. If time is missing this will be imputed as 00:00h
- If only the year is specified, and the year of the first dose of study medication is the same as the year of the start date, then the date of the first dose of study medication will be used. If this results in an imputed start date that is after the specified end date, then January 01, or the date of screening if this is later will be used (if the latter imputation results in an end date that is earlier than the start date, then January 01 will be used). If the imputed date is the date of first dose of study medication then time will be imputed as the start time of the study medication intake (i.e., event will be regarded as treatment-emergent)

The following rules will be applied to partial stop dates:

- If only the month and year are specified, then use the last day of the month
- If only the year is specified, then use December 31 of the known year
- If the stop date is completely unknown, do not impute the stop date

Missing or partially missing dates and/or times will be imputed as described in [Table 3-](#) .

Calculation rules for duration of adverse events can be found in [Table 3-](#) and will be applied for the calculation of duration of each AE. Adverse event duration is computed in and reported in day and time format: xx d hh:mm.

Table 3-2: Calculation rules for duration of adverse events

Data availability	Onset date/time	Outcome date/time	Calculation rules
Complete data	D1/T1	D2/T2	Duration = [(D2 – D1)*24 + (T2 – T1)]/24 d
End time missing	D1/T1	D2/--	End time is substituted by time 23:59h (=23.98 in decimal format) Duration = <[(D2 – D1)*24 + (23.98 – T1)]/24 d
Start time missing	D1/--	D2/T2	Onset time is substituted by time 00:00h Duration = <[(D2 – D1)*24 + T2]/24 d
Start and end time missing	D1/--	D2/--	Duration = <D2 – D1 + 1
Start day and time missing	--/--	D2/T2	Duration = [(D2 – D0)*24 + (T2 – T0)]/24 d For a participant in the FAS, D0 and T0 are the date and time of first administration of study medication and for screen failures, D0 is the date of the screening visit and T0 = 00:00h
End day and time missing	D1/T1	--/--	If the stop date is missing, duration will not be calculated.
Start and end date missing	--/--	--/--	If the stop date is missing, duration will not be calculated.

4.3 Handling of repeated and unscheduled measurements

All repeated and unscheduled measurements will be presented in the data listings, where applicable. The following general rules will apply to all repeated and unscheduled measurements:

- For repeated measurements obtained prior to the first dose of study medication the latest value (which may be scheduled or unscheduled) will be used in the calculation of the descriptive statistics
- For repeated measurements obtained at the designated Baseline visit, the latest value (which may be scheduled or unscheduled) will be defined as the Baseline provided that this occurred prior to the first dose of study medication

- Unscheduled and repeated measurements will not be used in the descriptive statistics at time points after first dose of study medication
- Unscheduled measurements performed for the End of Study/Early Termination Visit (EOS/ETV) visit will be assigned to the EOS/ETV Visit ([Section 4.4](#)) and analyzed accordingly as an EOS/ETV Visit.

4.4 Handling of measurements obtained at the early withdrawal visit

Study participants who withdraw early from the study for any reason, including those withdrawn from study medication, will be asked to return for the EOS/ETV Visit as soon as possible after the last dose of study medication.

4.5 Interim analyses and data monitoring

Not applicable.

4.6 Multicenter studies

This study is planned to be conducted at one site. Thus, there is no plan to explore sites effect in the analysis.

4.7 Multiple comparisons/multiplicity

Not applicable.

4.8 Use of an efficacy subset of participants

Not applicable.

4.9 Active-control studies intended to show equivalence

Not applicable.

4.10 Examination of subgroups

Not applicable

5 STUDY POPULATION CHARACTERISTICS

5.1 Participant disposition

The number of participants who signed the informed consent, participants who completed or prematurely discontinued the study, as well as the reason for discontinuation will be summarized for all participants, based on the SS. A participant who completed the study is defined as a study participant who completed all visits up to and including the EOS/ETV visit (in the Follow-up Period). If there is more than one termination due to AE, then an additional table summarizing the discontinuations due to AE will be produced. In case that only one subject discontinues due to AE, then this will be presented in a listing.

The number and percentage of study participants included in each of the analysis sets will be summarized based on All Study Participants. Percentages will be calculated based on All Study Participants for the purpose of this summary.

Screening failure reasons will be listed for the All Study Participants.

In addition, the following listings will be presented:

- Participant disposition (All Study Participants)
- Participant analysis sets (All Study Participants)

The listing of participant disposition will include the date of informed consent, date and time of first and last dose of study medication, date of premature termination and primary reason (if applicable).

5.2 Protocol deviations

Important protocol deviations will be identified and classified by the deviation types in the IPD document (see also section 3.4). A listing of all IPDs identified at the DEM will be presented by cohort for all participants based on the FAS and will include the deviation type and description.

6 DEMOGRAPHICS AND OTHER BASELINE CHARACTERISTICS

6.1 Demographics

A by-participant listing of demographics will be presented by cohort (Cohort A, Cohort B) based on All Study Participants. This will include the year of birth, age (in years), sex, race, ethnicity, country, height (in cm), weight (in kg) body mass index (BMI, in kg/m²). The body weight will be the measurement obtained at Screening. Body mass index (kg/m²) is documented in the CRF.

All demographic characteristics (except for year of birth) will be summarized by cohort and overall (Cohort A, Cohort B and All Study Participants) for all participants based on the FAS. The summary of age will include descriptive statistics and categorical summaries, the latter based on requirements for European Union Drug Regulating Authorities Clinical Trials (EudraCT) and clinicaltrials.gov reporting.

For the EudraCT reporting, the categories will include:

- 18 to <65 years
- 65 to <85 years
- ≥85 years

For clinicaltrials.gov reporting, the categories will include:

- ≤18 years
- 19 to <65 years
- ≥65 years

6.2 Other Baseline characteristics

The criteria to determine the Child-Pugh score will be summarized for all participants by cohort and overall based on the FAS. This includes total serum bilirubin (mg/dL), serum albumin

(g/dL), prothrombin time (sec prolonged/international normalized ratio (INR)), ascites, hepatic encephalopathy, total points and hepatic insufficiency classification.

6.3 Medical history, procedure history and concomitant medical procedures

Medical history will be listed and summarized (in an incidence table) for the SS, by MedDRA system organ class (SOC) and preferred term (PT). The reported term will be included in the listing. The summary will include the number and percentage of study participants, and will be sorted alphabetically by SOC and by descending incidence of PT within each SOC, based on the 'All Participants' column.

6.4 Prior and concomitant medications

Prior medications include any medications that started prior to the date of first dose of PSL. Concomitant medications are medications taken after the first dose of PSL and/or the SFU Period. Concomitant medications will be attributed to the treatment period in which they start. Thus, any medication taken on Day 1 through Day 7 will be attributed to the Single Dose Period; any medications taken after the first dose of PSL on Day 8 through Day 18 (including SFU) will be attributed to the Multiple Dose Period.

If a medication starts prior to PSL administration and stopped after the first PSL administration or stopped during the Single Dose Period, then that medication will be classified as both prior and concomitant for Single Dose Period only. If a medication starts prior to PSL administration and is stopped during the Multiple Dose Period, then that medication will be classified as prior and concomitant for both Single and Multiple Dose Periods.

Any medications with missing dates and/or times will be handled as described in [Section 4.2.4](#) to classify them as prior or concomitant.

Prior and concomitant medications will be listed for all participants in the SS. Prior and concomitant medication will be tabulated separately. The summary will be presented by WHODD Anatomical Main Group [Level 1 term text], Pharmacological Subgroup [Level 3 term text] and PT. The reported term will be included in the listing. Tabulation for prior medications will be presented by cohort; tabulation for concomitant medications will be summarized by treatment period and by cohort.

All tabulations will be sorted alphabetically by Level 1 term, alphabetical Level 3 term within Level 1 and decreasing frequency of PT in the 'All Participants' column.

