### **6.5 Concomitant medication(s)/treatment(s)**

#### **6.5.1 Permitted concomitant treatments (medications and therapies)**

The use of concomitant medications during this study by participants without hepatic insufficiency should be avoided unless necessary to treat AEs or unless approved on a case-by-case basis prior to enrollment (eg, hormonal contraceptives). The use of any concomitant medications should be approved by the Sponsor in advance, in writing, when possible. The following concomitant medications are permitted during the study:

- Paracetamol for the treatment of mild symptoms (eg, headache or other pain), given at most every 6h to 8h, not exceeding 2g/day, and with a total of no more than 10g over 15 days.
- Inhaled corticosteroids for seasonal rhinitis.
- Oral contraceptives not exceeding 30µg ethinyl estradiol or postmenopausal HRT or implants, patches, or IUDs/IUSs delivering progesterone (for female participants).

Use of other chronic medication by study participants with moderate hepatic insufficiency, not interfering with the endpoints of the study and at the discretion of the UCB Study Physician, will be permitted.

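### SAP 6.4 gives conflicting and incomplete rules for assigning concomitant medications to the Single-Dose and Multiple-Dose Periods

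*SAP*

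**What the plan says.** SAP 6.4 treats as concomitant any drug taken after the first padsevonil dose and tabulates these drugs by period and cohort. Four statements govern the assignment to a period:

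- **Start rule:** "Concomitant medications will be attributed to the treatment period in which they start".
- **Taken rule**, worded as a consequence of the start rule. For the first week it reads: "Thus, any medication taken on Day 1 through Day 7 will be attributed to the Single Dose Period". The later days are handled in the same way, by when the drug is taken: "any medications taken after the first dose of PSL on Day 8 through Day 18 (including SFU) will be attributed to the Multiple Dose Period".
- **First carry-over rule**, for a drug begun before padsevonil and stopped either after the first administration or within the Single-Dose Period: it "will be classified as both prior and concomitant for Single Dose Period only".
- **Second carry-over rule**, for a drug also begun before padsevonil but with its stop date in the later of the two periods: "that medication will be classified as prior and concomitant for both Single and Multiple Dose Periods".

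SAP 4.2.4, which 6.4 cites for missing dates, adds: "If the stop date is completely unknown, do not impute the stop date".

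Protocol 6.5.1 asks participants without hepatic insufficiency to avoid concomitant medication, with listed exceptions. It also permits, at the discretion of the sponsor's study physician, "Use of other chronic medication by study participants with moderate hepatic insufficiency", provided that it does not interfere with the endpoints.

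**The concern.** Assigning by start suits an adverse event, which has an onset, and SAP 10.2 uses such a rule for adverse events. A medication is an exposure over an interval, and what matters is whether it was on board during the period. The Multiple-Dose column should therefore show every drug taken from Day 8 onward, including during the Day 12 profile. A start rule cannot do that for a drug begun earlier, and the two carry-over rules repair it only in part.

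The taken rule would place these drugs correctly, but it is presented as following from the start rule and gives a different answer. Two programmers could each follow SAP 6.4 faithfully and produce different tables. Drugs that span both periods are to be expected mainly in Cohort B, so any undercount would fall mainly there.

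**Working it through.** There is no figure to reproduce. The check puts each start and stop pattern through each rule in SAP 6.4. In the table, single stands for the Single-Dose Period, multiple for the Multiple-Dose Period, and both for the two together. A dash means that the carry-over rule's condition is not met.

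| Start | Stop | Start rule | Taken rule | First carry-over | Second carry-over |
|---|---|---|---|---|---|
| Before Day 1 | Days 1 to 7, after the first dose | neither | single | single only | – |
| Before Day 1 | Days 8 to 18 | neither | both | single only (literal fit) | both |
| Before Day 1 | None by Day 18 | neither | both | – | – |
| Days 1 to 7 | Days 1 to 7 | single | single | – | – |
| Days 1 to 7 | After the first Day 8 dose | single only | both | – | – |
| After the first Day 8 dose | At any time | multiple | multiple | – | – |

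The fourth and sixth rows raise no problem. In the first row, the first carry-over rule settles the matter and agrees with the taken rule. The other three rows are the patterns in which a drug was taken in the Multiple-Dose Period but began earlier:

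1. **Begun before Day 1, stopped on Days 8 to 18.** The second carry-over rule gives both periods. The first alternative in the first carry-over rule (stopped after the first administration) has no upper time limit, so it also fits and gives the Single-Dose Period only. The two rules overlap with different results.
2. **Begun before Day 1, no stop by Day 18.** The drug was never stopped, so neither carry-over rule applies. Because SAP 4.2.4 leaves a completely unknown stop date unimputed, imputation cannot satisfy the second rule either. The start rule gives no period and the taken rule gives both.
3. **Begun on Days 1 to 7, continued past Day 8.** Both carry-over rules require a start before padsevonil, so neither helps. The start rule leaves the drug out of the Multiple-Dose column and the taken rule includes it.

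The second pattern is the plausible one for Cohort B. Exclusion criterion 35 in Protocol 5.2 requires drugs for the care of hepatic insufficiency (apart from limited paracetamol) to have been established in dose and schedule for at least 14 days before the first liver function test. They therefore begin before Day 1, and maintenance treatment may well have no stop date by Day 18.

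**The case against.** The best defence is that the taken rule states how the section is meant to be applied. On that reading, all three patterns are counted in both periods and nothing is lost. The second carry-over rule points the same way: it would be odd to carry a drug forward if it was stopped on Day 14 but drop it if it was never stopped. The section's own definition of a concomitant medication also goes by when a drug is taken. This is a fair account of the likely intent, and it means that wrong counts are possible, not certain. It does not remove the contradiction, because the start rule is stated without qualification and comes first.

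The third pattern should also be uncommon. Protocol 6.5.2 prohibits non-permitted medicines during the study unless needed to treat an adverse event. That limits the frequency, not the defect in the rule.

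A reader might infer three stronger conclusions that the documents do not support:

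- **That the cohorts would look alike in co-medication.** Drugs begun before the first dose are prior medications, and SAP 6.4 tabulates these by cohort. The Safety Set listing also keeps every drug, in a study of up to 24 participants.
- **That Cohort B's chronic drugs would all vanish from the Multiple-Dose column.** This requires the taken rule to be ignored, and neither document says how many participants take such drugs.
- **That the Day 12 primary endpoints are affected.** SAP 9.1 compares cohorts by ANOVA without using medication, SAP 4.1 plans no covariate adjustment, and exclusion from the PK Set depends on important protocol deviations (SAP 3.4 and 3.5.4). None of these uses the period assignment.

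**Conclusion.** The point holds as a defect in a reporting rule. SAP 6.4 states a start rule that its next sentence contradicts, and its carry-over rules are both incomplete and overlapping. Of the three patterns in which a drug taken in the Multiple-Dose Period began earlier, one drops out under the start rule, one meets no carry-over rule, and one meets two that disagree.

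The consequence is possible miscounting in the descriptive concomitant-medication table by period and cohort, and nothing beyond it. The number of participants affected cannot be derived from the documents. That the miscounting would fall mainly on Cohort B is an inference from the medication rules in the protocol. Cohort A may contribute too, for example through approved hormonal contraceptives. The correction is minor but worth making before the table is programmed.

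**What to change.** In SAP 6.4, delete the start-date sentence and the two carry-over sentences, and use one overlap rule in place of the present wording:

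- A medication is concomitant for the Single-Dose Period if it was taken at any time from the Day 1 dose to the Day 8 predose.
- It is concomitant for the Multiple-Dose Period if it was taken at any time from the first Day 8 dose to Day 18.
- It may count in both periods.
- For this classification only, a medication that is ongoing or has a completely unknown stop date is treated as continuing to Day 18.

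The last line should cross-refer to SAP 4.2.4, so that it is not read as changing the rule against imputing an unknown stop date; listings would still show dates as reported. A table footnote should say that a participant can appear in both period columns.

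The cost is a few sentences and a simple programming rule, with no new data. Treating an unknown stop date as ongoing could overcount slightly, but the listing lets a reader check each case.

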7 MEASUREMENTS OF TREATMENT COMPLIANCE

Administration of PSL will be performed under the supervision of the Investigator (or designee) and the Investigator (or designee) will check the study participant's hands and the oral cavity immediately after dosing to confirm ingestion of the study medication. Compliance will be monitored by drug accountability and by drug assay for PSL (using the drug concentration in the blood/plasma). A Drug Accountability form will be used to record study medication dispensing and return information on a by-participant basis. Compliance with the study medication is defined as consumption by the study participant that confirms 100% with the planned dosage.

Drug administration/consumption will be recorded and any discrepancies with the dosing regimen will be explained. Dosing deviations will be included in the listing of IPDs where applicable.

No formal calculations of compliance will be presented as all study medication is administered on site.

8 EFFICACY ANALYSES

Not applicable.

9 PHARMACOKINETICS

The calculation of the PK parameters of PSL and two of its metabolites ([REDACTED] and [REDACTED]) will be performed by the Pharmacokinetics, Pharmacodynamics, Modeling and Simulation Department, [REDACTED]. All PK TFLs will be produced by [REDACTED] programming (Early Phase) or [REDACTED].

Pharmacokinetic concentrations and PK parameters of PSL and two of its metabolites ([REDACTED] and [REDACTED]) will be summarized by treatment period (SD and MD) and cohort (healthy participants and participants with moderate hepatic impairment) based on the PKS.

Pharmacokinetic parameters of PSL and two of its metabolites ([REDACTED] and [REDACTED]) will be computed using the actual sampling time points.

Urine concentration of PSL and two of its metabolites ([REDACTED] and [REDACTED]) and amount of PSL and two of its metabolites excreted will be listed by treatment period, cohort, and by study participant on the PKS.

9.1 Analysis of the primary pharmacokinetic variables

All deviations will be calculated relative to the last dose of study medication (on Day 1 for Single Dose Period and on Day 12 for Multiple Dose Period). Any samples that are obtained outside the tolerance window permitted at the specified time point will be discussed at the DEM and any possible exclusion from analysis will be documented accordingly. The primary PK variables in plasma used for PSL are: C_{max} , AUC_{0-t} and AUC for the Single Dose Period and $C_{max,ss}$ and AUC_{τ} for the Multiple Dose Period. C_{max} and $C_{max,ss}$ will be determined from the observed concentration and time data. AUC_{τ} , AUC and AUC_{0-t} will be computed using the linear up/log down trapezoidal rule.

The PK plasma concentrations and the primary PK parameters of PSL will be summarized by period, cohort, and nominal sampling times using descriptive statistics (number of available observations [n], arithmetic mean, median, standard deviation, minimum, maximum, geometric mean, geometric CV and 95% CI for the geometric mean [assuming log-normally distributed data]). Values below the LLOQ will be reported with a clear sign (flag variable in the dataset) indicating that they were below the LLOQ.

Individual participant concentration-time profiles of PSL will be displayed graphically in linear and semi-logarithmic scale. Combined individual (spaghetti) plots will be displayed by treatment period, cohort and analyte with all participants overlaid on the same plot (linear and semi-logarithmic scale).

Geometric mean profiles of plasma concentrations for PSL over time will be presented, with all cohorts overlaid on the same plot, in both linear and semi-logarithmic scale for each treatment period. For the linear scale plot only, the lower and upper 95% confidence interval (CI) for the geometric mean will be displayed.

All plasma concentration figures will include the LLOQ on the semi-logarithmic scale plots and will be based on scheduled times.

For Cohort B only, the relationship between the primary PK parameters and the Child-Pugh parameters (total serum bilirubin, serum albumin, and prothrombin time (sec prolonged)) will be displayed graphically using scatter plots. This relationship will be evaluated further using linear regression, where PK parameter is the dependent variable and the Child-Pugh parameters are included as fixed effects. However, data from the linear regression analysis will be presented in a separate report.

For the Single and Multiple Dose Periods, primary PK parameters of PSL will be compared between the cohorts (healthy participants and participants with moderate hepatic impairment) using analysis of variance (ANOVA) as follows: point estimates for the ratio of geometric means between healthy participants and participants with moderate hepatic impairment and the respective 2-sided 90% CIs will be computed using the least squares means and the root mean squares of error from the ANOVA of the log-transformed data with subsequent exponential transformation. Interstudy participant variability of PK parameters will be derived from these analyses.

